## 4.2 EXCLUSION CRITERIA

- 1) Prior treatment with plitidepsin.
- 2) Concomitant diseases/conditions:
  - a) History or presence of angina, myocardial infarction, clinically relevant valvular heart disease, uncontrolled hypertension, or congestive heart failure within the previous 12 months.
  - b) Symptomatic arrhythmia (excluding grade  $\leq 2$  anemia-related sinus tachycardia) or any arrhythmia requiring ongoing treatment, and/or prolonged grade  $\geq 2$  QT-QTc, or presence of unstable atrial fibrillation. Patients with stable atrial fibrillation on treatment are allowed provided they do not meet any other cardiac or prohibited drug exclusion criterion.
  - c) History (or family history) of long QT syndrome.
  - d) Corrected QT interval (QTcF, Fridericia correction)  $\geq$  grade 2 on screening electrocardiogram (ECG).
  - e) Clinically significant resting bradychardia, or history of syncope.
  - f) History or presence of ventricular arrhythmias, including ventricular tachycardia or Torsades de Pointes.
  - g) Patients receiving treatment with any medication with known risk of producing Torsade de Pointes (see [Appendix 8](#)).
  - h) Active uncontrolled infection. Active hepatitis B or C virus (HBV or HCV), or human immunodeficiency virus (HIV) infection.
  - i) Morphological or cytological features of myelodysplasia and/or post-chemotherapy aplasia on BM assessment.
  - j) Myopathy  $>$  grade 2 or any clinical situation that causes significant and persistent elevation of CPK ( $> 2.5 \times$  ULN in two different determinations performed one week apart).
  - k) Limitation of the patient's ability to comply with the treatment or follow-up requirements.
  - l) Diagnosis of another invasive malignancy unless free of disease for at least three years following therapy with curative intent. Patients with early-stage basal cell or squamous cell skin cancer, cervical intraepithelial neoplasia, cervical carcinoma *in situ*, or superficial bladder cancer, may be eligible to participate at the Investigator's discretion.
  - m) Any other major illness that, in the Investigator's judgment, will substantially increase the risk associated with the patient's participation in this study.
- 3) Central nervous system (CNS) involvement.
- 4) Women who are pregnant or breast feeding. Fertile patients (men and women) who are not using an effective method of contraception. All patients (men and women) must agree to use an effective contraceptive measure (if applicable) up to six months after treatment discontinuation. Valid methods to determine the childbearing potential, adequate contraception and requirements for women of childbearing potential (WOCBP) and their partners are described in [Appendix 6](#).
- 5) Concomitant medications that include corticosteroids, chemotherapy, or other therapy that is or may be active against AITL, within the two weeks prior to treatment start. Concurrent corticosteroids are allowed, provided they are

administered at an equivalent prednisone dose of  $\leq 10$  mg daily, as premedication for blood products and/or for the relief of the symptoms derived from the disease.

- 6) Major upper gastrointestinal bleeding episode occurring during the previous year before screening.
- 7) Known hypersensitivity to any of plitidepsin's formulation components (See Section [7.1.1](#), Study Drug Formulation).

## 5. PLAN OF THE STUDY

### 5.1 PLANNED TRIAL PERIODS (FOR THE WHOLE STUDY)

The total duration of the study will be approximately 42 months.

**Planned start date** (first patient on study): 2Q2016.

**Planned enrollment period**: 36 months.

**Planned end-of-study date** (clinical cutoff): 12 months after the last patient's inclusion. If there are patients still being treated at the planned cutoff date, the actual cutoff date will be the date when those patients have completed the ongoing treatment cycle and the corresponding EOT visit.

The study will be closed earlier than planned if less than 15 patients are recruited in the first year after most of the sites are in active enrollment. Recruitment reviews will continue annually to assess the feasibility of meeting the study objectives and study continuation.

[figure not shown]
### 5.2 PLANNED TRIAL PERIODS (INDIVIDUALLY PER PATIENT)

Patients will be evaluated at scheduled visits in three study periods:

- **Pretreatment:** from signature of the informed consent to the first dose of study treatment.
- **Treatment:** from first dose of study treatment to EOT (see Section [5.2.1.1](#)). EOT is defined as 30 days ( $\pm$  one week) after the day of last administration of study treatment or as soon as possible after End of Cycle 6 radiological and clinical assessments (if the patient discontinues: see [Figure 3](#) below), unless the patient starts a new antitumor therapy or dies within 30 days from the last dose, in which case the date of administration of this new antitumor therapy or the date of death will be considered the EOT date.
- **Follow-up:** after EOT, patients will be followed every four weeks until resolution of all toxicities (if any). Patients who discontinue treatment without progression will be followed every four months (+ two weeks) for the first two years of follow-up, and every six months (+ two weeks) thereafter, unless clinically indicated, until PD, start of other antitumor therapy, death or the date of study termination (clinical cutoff), whichever occurs first. After documented progression or start of a new antitumor therapy, patients will be followed for survival approximately every four months during the first two years, and then approximately every six months until death or the date of study termination, whichever occurs first. For the purpose of collecting information on patient's survival exclusively, a documented telephone call is acceptable; follow-up for survival will be completed for all patients only if results of the primary endpoint confirm the trial as positive.

Patients will be considered to be **on-study** from the signature of the informed consent form (ICF) to the end of the follow-up period (or screening failure). Investigators can appraise potential study candidates in a pre-screening period but only perform study-specific screening assessments after the patient formally consents. Patients will be considered to be **on-treatment** from the date of first dose until EOT.

**Figure 3.** Study design.

Central pathological review involves different analyses in two separate processes: (a) of local histopathology reports before approving patient inclusion, and (b) of tumor samples before each futility analysis and at the end of study.

CR, complete response; D, day; EOT, end of treatment; ICF, informed consent form; PD, progressive disease; PR, partial response; SD, stable disease; wk, week.

Patients may withdraw their consent at any time; if consent to study participation is withdrawn, no further study activities will be conducted on them ([5.2.1.3 Study Discontinuation](#)). If consent only to the study treatment is withdrawn, treatment will be stopped and other study procedures performed as normal (see [5.2.1.1](#) below).

## **5.2.1 Discontinuations**

### **5.2.1.1 Treatment Discontinuation**

Treatment discontinuation occurs when an enrolled patient ceases to receive plitidepsin regardless of the circumstances. By convention, the date of the end of treatment is defined as 30 days after the day of the last dose of plitidepsin (treatment discontinuation), the start of a new antitumor therapy or death, whichever occurs first, in which case the date of administration of this new therapy or the date of death will be considered the date of EOT. In this study, however, EOT will also be conditioned by an End of Cycle 6 visit in which a radiological assessment 4–8 weeks after the last dose of Cycle 6 will determine whether treatment can continue to Cycle 7.

The primary reason for any treatment discontinuation will be recorded on the patient's Case Report Form (CRF).

If a patient discontinues treatment, every effort should be made to complete the scheduled assessments as appropriate, whenever possible.

### **5.2.1.2 Reasons for Treatment Discontinuation**

Patients will receive study treatment until:

- Disease progression (PD).
- Maximum of six cycles unless the patient is in:
  - PR 4–8 weeks after last dose of Cycle 6: in accordance with Investigator decision, the patient may then continue in treatment until CR or progression.
  - SD 4–8 weeks after last dose Cycle 6: in accordance with Investigator decision, the patient may then continue until CR or progression.
- If patient is in CR after six treatment cycles, treatment should be stopped.
- The patient achieves PR or CR at any time during the planned six cycles and is eligible for consolidation with autologous or allogeneic stem cell transplant (SCT) as per Investigator criteria.
- There is unacceptable toxicity.
- There is intercurrent illness of sufficient magnitude to preclude safety continuation of the study.
- There is patient refusal and/or non-compliance with study requirements.
- Investigator's decision.
- There is a protocol deviation with an effect on the risk/benefit ratio management of the patient.
- There is a treatment delay > 15 days from the treatment due date (except in case of clear clinical benefit and with the Sponsor's approval).
- There is a requirement of > 2 dose reductions (except in case of clear clinical benefit and with the Sponsor's approval).

Patients who are withdrawn for any reasons must not be re-treated in the context of this study at any time. For follow-up activities, please refer to Section [5.11](#).

### **5.2.1.3 Study Discontinuation**

Study discontinuation occurs when an enrolled patient ceases to participate in the study, regardless of the reason (as detailed under “Follow-up” in Section 5.2). Patients have the right to withdraw consent at any time; if this is the case, no further study procedures should be performed.

The date and reason for study discontinuation will be clearly documented on the patient’s CRF.

### **5.2.2 Protocol Deviations**

A protocol deviation is defined as any departure from what is described in the protocol of a clinical trial approved by an Independent Ethics Committee (IEC)/Institutional Review Board (IRB) and the Competent Authorities. Therefore, it applies to deviations related to patient inclusion and clinical procedures (e.g., assessments to be conducted or parameters to be determined), and also to other procedures described in the protocol that concern Good Clinical Practice (GCP) guidelines or ethical issues (e.g., issues related to obtaining the patients’ Informed Consent, data reporting, Investigator’s responsibilities, etc.).

Deviations with no effects on the risk/benefit ratio of the clinical trial (such as minimal delays in assessments or visits) will be distinguished from those that might have an effect on this risk/benefit ratio, such as:

- Deviations that might affect the clinical trial objectives, such as those involving inclusion/exclusion criteria (which could mean that the patient is not eligible for the trial) and those having an effect on patient’s evaluability.
- Deviations that might affect the patient’s well-being and/or safety, such as incorrect dosing of the investigational medicinal product (plitidepsin) due to not following dose adjustment specifications or an incorrect preparation of the medication.
- Deviations related to the following of GCP guidelines as described in the protocol and regulations in force, such as deviations when obtaining the Informed Consent or not following the terms established for reporting Serious Adverse Events, etc.

As a general rule, NO deviations that may have an effect on the risk/benefit ratio of the clinical trial will be authorized. All protocol deviations detected during the study will be appropriately documented, and those considered particularly relevant (i.e., those related to ethical issues, fulfillment of GCP guidelines and with an effect on the risk/benefit ratio) will be notified to the pertinent IEC/IRB and, if applicable, to the Competent Authorities as established by local regulations.

Failure to attend the EOT visit exclusively due to a deteriorated clinical condition will not be considered a protocol deviation.

Furthermore, non-availability or non-evaluability of a diagnosis or re-biopsy specimen for central pathological review will not be considered a deviation (given that, in some instances, re-biopsy may not be feasible because of disease location) but eligibility must first be confirmed with the sponsor prior to inclusion.

## **5.3 ADDITION OF PATIENTS**

All eligible and treated patients with AITL diagnosis confirmed after central pathological review will be included in the main efficacy analyses (primary and secondary endpoints).

If a patient is treated but AITL diagnosis is not finally confirmed after central pathological review of the biopsy (even if inclusion was approved on the basis of the local histopathological report) then an additional patient will be included. Specifically, cases with features of follicular-PTCL and PTCL-NOS with TFH phenotype or with features of progression/transformation from AITL to Diffuse Large B-cell Lymphoma need to be excluded from the main efficacy analysis so additions are permitted in the event such patients are included before (or in spite of) central pathological exclusion. All patients without central confirmation will be excluded from the main efficacy analyses but included in safety analyses and, as supportive analyses, efficacy assessments will be done including all treated patients.

#### 5.4 PRETREATMENT ASSESSMENTS

During the pretreatment (or screening) period, following signature of the Informed Consent Form, the Investigator will assess the patient's eligibility for inclusion in the study by conducting the assessments summarized below. The Sponsor must confirm eligibility before the patient starts treatment: see also [Figure 3. Study design](#).

**Table 4.** Screening period: pretreatment assessments.

	ASSESSMENT	TIME
1. Written informed consent	The informed consent process involves an explanation and discussion with the patient including time for questions and answers and culminates in signing and dating the consent form if the patient agrees. Document participation in the patient's medical chart as well.	Before any study-specific procedures.
2. Medical and cancer history/ clinical examination	
 
◆ Demographic data (race/ethnicity [if permitted], age, sex, height).
 
◆ Medical and cancer history/baseline condition:               
 
○ Primary diagnosis.
 
○ Prognostic factors at first diagnosis.*
 
○ Prior treatments (with best response and TTP, when available).
 
○ Documented date of relapse or refractory disease.
 
○ Ann-Arbor staging (see Appendix 5)
 
 
 
	Within 28 days prior to Day 0.
	
 
◆ Complete physical examination, including weight and BSA.
 
◆ Basic neurological examination.
 
◆ Performance status (ECOG PS).
 
◆ Vital signs: heart rate, blood pressure and body temperature.
 
◆ Concomitant therapies.
 
	Within 14 days prior to Day 0.

8. Bone marrow biopsy/aspirate		Within 14 days prior to Day 0.
9. Chest X-ray	If needed.	Within 28 days prior to Day 0.
10. Tumor assessment	Radiological (PET-CT + CT *** ) and clinical tumor assessment.	Within 28 days prior to Day 0.
11. Adverse events	Clinical assessment of the patient's signs and symptoms (if any and including nurses' assessment and patient-reported issues) should continue on an ongoing basis throughout the study and be reported at least every cycle as AEs: between IC and Day 0, AEs are considered baseline and non-treatment emergent. Grading should be as per the NCI-CTCAE v.4.	Within 14 days prior to Day 0.

\* Prognostic Index for Peripheral T-cell lymphoma (PIT) uses four variables as predictive for survival: age, PS, LDH level and BM involvement ([Appendix 3](#)). The standard International Prognostic Index (IPI) comprises the following variables: age  $\geq$  60 years, disease stages III to IV, LDH > normal, ENSs > one and PS  $\geq$  2. The alternative Prognostic Index for AITL (PIAI) comprises the following factors: age  $\geq$  60 years, PS  $\geq$  2, ENSs > one, B symptoms and platelet count  $<150 \times 10^9/L$  ([Appendix 4](#)).

\*\* Hematology and Biochemistry-A, -B not to be repeated prior to C1D1 if performed within the seven previous days and there are no changes in the patient's clinical status and medications.

\*\*\* When PET-CT is performed it must be in combination with diagnostic quality CT with intravenous contrast (except medically contraindicated). Two alternatives are allowed: Hybrid PET CT scanners may be used to acquire diagnostic quality CT which includes intravenous contrast OR PET CT without intravenous contrast and diagnostic quality CT images with intravenous contrast using a standalone CT scanner must be performed.

ALT, alanine aminotransferase; ALP, alkaline phosphatase; AST, aspartate aminotransferase; BSA, body surface area; CPK, creatine phosphokinase; CPK-MB, creatine phosphokinase-isoenzyme MB; ECG, electrocardiogram; ECOG, Eastern Cooperative Oncology Group;  $\beta$ -hCG, beta subunit of human chorionic gonadotropin; INR, international normalized ratio; LDH, lactate dehydrogenase; NCI-CTCAE, National Cancer Institute Common Terminology Criteria for Adverse Events; PS, performance status; PT, prothrombin time; PTT, partial thromboplastin time; SAE, serious adverse event; TTP, time to progression; WBC, white blood cells; WOCBP, woman of childbearing potential.

## 5.5 PATIENT REGISTRATION

The patient will be allocated a patient number in the e-CRF after signing the ICF and screening begins. This patient number should be used on all future documentation and correspondence referring this patient. Eligibility will be checked before inclusion and registration (approval from the central pathological review of the local histopathology report) confirmed by the Sponsor. The patient will be a screening failure if not all inclusion criteria are met, if any exclusion criterion is met, if central pathological review of the local histopathology report does not confirm the AITL diagnosis, or if the Sponsor does not approve inclusion. Regardless of circumstances, Investigators will not

be allowed to treat any patient before appropriate receipt of the Sponsor's agreement to proceed with inclusion: see also [Figure 3. Study design](#).

A patient who has been treated without the Sponsor's agreement will not be considered evaluable for the study and will need to be replaced (although can continue in treatment until discontinuation for any other reason).

For patients included in the study (all registered patients) but never treated, only baseline and off-study visit modules of the e-CRF should be completed.

For screen failures (patients who started screening but were not finally included), only the screening form of the e-CRF should be completed but SAEs occurring during screening need to be reported.

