## **8.2 SAFETY**

Patients will be evaluable for safety if they have received any partial or complete treatment cycle. All AEs will be graded according to the NCI-CTCAE, v.4 and will be coded using the Medical Dictionary for Regulatory Activities (MedDRA). Cycle delays, skipped doses, dose reduction requirements, and reasons for treatment discontinuation will be monitored throughout the study.

The safety profile of patients will be monitored throughout the treatment and up to 30 days after the last treatment dose (EOT), or until the patient starts a new antitumor therapy or until the date of death, whichever occurs first.

Any treatment-related AEs will be followed until recovery to at least grade 1 or stabilization of symptoms, whenever possible.

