4.1 Analysis sets definitions

“All Included Patients” analysis set is defined as all patients who are included in the study (excluding patients who signed informed consent but are classified as screening failures), independent of whether they received the study drug.

“All Treated Patients” analysis set is defined as all included patients who receive at least part of one dose or infusion of plitidepsin.

“Per Protocol Patients” analysis set is defined as all eligible and treated patients with AITL diagnosis confirmed after central pathological review.

“All Evaluable Patients” analysis set is define as all eligible patients with AITL diagnosis confirmed after central pathological review who receive at least two plitidepsin cycles in which at least two complete infusions have been administered and had at least one disease assessment as well as in patients who discontinue treatment without Cycle 3 tumor assessment after at least two plitidepsin infusions due to disease progression (PD) (or death due to PD) or toxicity (or death due to toxicity), defined as “early PD” and “treatment failures” respectively.

“All Responder Patients” analysis set is defined as all patients with CR or PR as overall best response.

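### The SAP safety set is limited to included patients, so it can drop a patient dosed without Sponsor approval, and the SAP efficacy sets do not say how to handle such a patient

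*Protocol*

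**What the plan says.** Protocol 5.5 contains four rules that bear on this point.

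- A patient is a screening failure if an entry criterion is not satisfied, if central review of the local report does not confirm AITL, "or if the Sponsor does not approve inclusion".
- A patient treated without the Sponsor's agreement "will not be considered evaluable for the study and will need to be replaced". The same sentence lets that patient stay on treatment.
- Included means registered: "For patients included in the study (all registered patients) but never treated".
- For screening failures, "only the screening form of the e-CRF should be completed", apart from reporting SAEs that occur during screening.

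SAP 4.1 builds the analysis sets. All Included leaves out screening failures. All Treated is "all included patients who receive at least part of one dose or infusion of plitidepsin". Per Protocol is "all eligible and treated patients with AITL diagnosis confirmed after central pathological review". All Evaluable adds exposure and assessment conditions for eligible, centrally confirmed patients. None of these definitions mentions Sponsor agreement. SAP 4.3 bases safety on All Treated.

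Elsewhere, safety evaluability depends on exposure alone. Protocol 8.2 states: "Patients will be evaluable for safety if they have received any partial or complete treatment cycle". SAP 7 likewise asks only that some study treatment was received.

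**The concern.** In a safety analysis, every dosed patient should count. Here the operative definition in the SAP depends on an administrative status, registration, which Protocol 5.5 itself expects can be missing in a dosed patient. The e-CRF rule for screening failures makes this worse: if it were applied to such a patient, exposure and on-treatment adverse events might never be collected, and a later change of definition could not recover them. All Treated is also a supportive efficacy set (SAP 4.2), so the same patient would drop out there too.

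On efficacy, the 5.5 rule to exclude and replace has no counterpart in the SAP. Protocol 5.3, which governs additions, foresees them only when AITL is not confirmed. In an open, single-arm trial response may be known before anyone decides what eligible means, so an undefined term leaves room for a choice that depends on the result. The Per Protocol set carries the primary endpoint and both futility tables.

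**Working it through.** **1. Set membership.** Take a patient who received plitidepsin and whom the Sponsor never approved or registered.

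| Text | Is the patient in? |
|---|---|
| Protocol 5.5, screening-failure rule | Screening failure if approval is refused |
| Protocol 5.5, included = registered | Not included |
| SAP 4.1 All Included | Out |
| SAP 4.1 All Treated, hence the SAP 4.3 safety set | Out, because it is restricted to included patients |
| Protocol 8.2 | In |
| SAP 7 | In |
| SAP 4.1 Per Protocol and All Evaluable | Not stated; depends on the meaning of eligible |

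The SAP therefore contradicts both the protocol and its own section 7. Because Per Protocol does not explicitly require inclusion, a patient could even be in Per Protocol but outside All Treated. Protocol 5.3 adds a related case. It foresees patients entering despite central pathological exclusion and wants all unconfirmed patients in the safety analyses, while 5.5 makes a patient whose local report fails central review a screening failure.

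**2. The plan's own figure.** Inputs from Protocol 9.1 and SAP 5: N = 60, success at 19 or more responders, lower 95% limit above 20%. The exact limits are: lower = the 0.025 quantile of Beta(x, n−x+1); upper = the 0.975 quantile of Beta(x+1, n−x).

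- 19/60 = 31.7%, limits 20.26% to 44.96%. This reproduces the stated 20.3% to 45.0%.
- 18/60 = 30.0%, lower limit 18.8%. So 19 is the minimum at N = 60.

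**3. One patient counted and also replaced.** Assume a non-responder who meets the entry criteria and is centrally confirmed. N becomes 61.

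- 19/61 = 31.1%, exact limits 19.9% to 44.3%. The lower limit is below 20%.
- 20/61 = 32.8%, lower limit 21.3%. So 20 responders are needed; the minimum is 19 for N = 57 to 60 and 20 for N = 61 to 64.

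If instead the patient is one of 19 responders and is excluded and replaced by a non-responder, the result is 18/60, which fails.

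**4. The same case on the normal test.** Protocol 9.2.1 calculates the final test statistic from the normal distribution, and 9.1 puts the variance under the null: z = (p − P0)/√(P0(1 − P0)/n).

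- P0 = 0.208: (0.3115 − 0.208)/√(0.208 × 0.792/61) = 1.99.
- P0 = 0.20: (0.3115 − 0.20)/√(0.20 × 0.80/61) = 2.18.

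Both exceed 1.96, so 19/61 still rejects the null hypothesis.

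**5. Safety illustration.** Assume 60 dosed patients, one of them unapproved, and that this patient has the only event of some type. Counted, the rate is 1/60 = 1.7% (exact 95% limits 0.04% to 8.9%). Dropped, it is 0/59 (0% to 6.1%), and the event disappears from the table.

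**The case against.** The best defence of the safety definition is that 5.5 deals with two different patients. Screening failures, in its own gloss, began screening but were not finally included; a patient who continues treatment and is replaced does not fit that description. Dosing before the agreement arrives also differs from dosing after a refusal, and a patient registered later would be included. Protocol 8.2 and SAP 7 state the intent without conditions. All this is fair, and nobody need suppose that the Sponsor means to drop dosed patients. But even a patient who is not a screening failure is outside All Treated if never registered, because 5.5 equates included with registered. The intent stated elsewhere conflicts with the operative definition and does not correct it.

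A second defence is that SAP Listings 10.1.2 (exclusions from populations) and 10.3.1 (deviations) would show such cases. However, SAP section 10 is itself run on All Included, so the listings share the gap.

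On efficacy, a reader might infer that the Per Protocol definition keeps these patients and that the primary denominator therefore differs between documents. The texts do not establish this. Per Protocol admits only eligible patients, and Protocol 5.4 says "The Sponsor must confirm eligibility before the patient starts treatment", so a consistent reading excludes them, as 5.5 does. A patient who fails an entry criterion is out on either reading. On the other side, SAP 4 ties inclusion to the entry criteria alone. What stands is that the SAP is silent and its key term is undefined.

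**Conclusion.** The safety point holds as written: read literally, SAP 4.1 with Protocol 5.5 can drop a dosed patient from the safety set, against Protocol 8.2 and SAP 7. It rests on 5.5's equation of included with registered and needs no assumption about frequency.

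The efficacy point is secondary and is an omission: SAP 4.1 neither adopts nor rejects the 5.5 rule. It would be tempting to call a single such patient decisive for the trial. That is true only on the exact-interval criterion, only with exactly 19 responders, and only if a centrally confirmed non-responder is both counted and replaced; the normal test still rejects. The documents give no expected number of such patients, and since 5.5 forbids the situation it may be zero.

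**What to change.** - **SAP 4.1:** define All Treated as every patient who received any amount of plitidepsin, whatever the registration or screening status.
- **Protocol 5.5:** state that the screening-form-only e-CRF rule does not apply to a patient who has been dosed.
- **Protocol 5.5 and SAP 4.1:** define eligible, and reconcile the passages with one rule fixed before response is known. Either carry the 5.5 exclusion into the Per Protocol and All Evaluable definitions, or remove it from 5.5. Both remove the contradiction and ensure that nobody is both counted and replaced. Keeping such patients without replacing them would reverse an explicit protocol rule, and the documents give no ground for preferring that option.

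The cost is a few sentences. The design, sample size and success threshold do not change. The only extra data are full e-CRF pages for any patient dosed without approval, for whom Protocol 8.2 already requires safety evaluation.
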